## 10.4 Storage and Handling Requirements

Clinical supplies must be stored in a secure, limited-access location under the storage conditions specified on the label.

Receipt and dispensing of trial medication must be recorded by an authorized person at the trial site.

Clinical supplies may not be used for any purpose other than that stated in the protocol.

## 10.5 Returns and Reconciliation

The investigator is responsible for keeping accurate records of the clinical supplies received from Merck or designee, the amount dispensed to and returned by the participants and the amount remaining at the conclusion of the trial.

Upon completion or termination of the study, all unused and/or partially used investigational product will be destroyed at the site per institutional policy. It is the Investigator's responsibility to arrange for disposal of all empty containers, provided that procedures for proper disposal have been established according to applicable federal, state, local and institutional guidelines and procedures, and provided that appropriate records of disposal are kept.

**APPENDIX A. ECOG PERFORMANCE STATUS**

Grade	Description
0	Normal activity. Fully active, able to carry on all pre-disease performance without restriction.
1	Symptoms, but ambulatory. Restricted in physically strenuous activity, but ambulatory and able to carry out work of a light or sedentary nature (e.g., light housework, office work).
2	In bed <50% of the time. Ambulatory and capable of all self-care, but unable to carry out any work activities. Up and about more than 50% of waking hours.
3	In bed >50% of the time. Capable of only limited self-care, confined to bed or chair more than 50% of waking hours.
4	100% bedridden. Completely disabled. Cannot carry on any self-care. Totally confined to bed or chair.
5	Dead.
* As published in Am. J. Clin. Oncol.: Oken, M.M., Creech, R.H., Tormey, D.C., Horton, J., Davis, T.E., McFadden, E.T., Carbone, P.P.: Toxicity And Response Criteria Of The Eastern Cooperative Oncology Group. Am J Clin Oncol 5:649-655, 1982. The Eastern Cooperative Oncology Group, Robert Comis M.D., Group Chair.	

## APPENDIX B. COMMON TERMINOLOGY CRITERIA FOR ADVERSE EVENTS V4.0 (CTCAE) AND LEE 2014 CRS CRITERIA

The descriptions and grading scales found in the revised NCI Common Terminology Criteria for Adverse Events (CTCAE) version 4.0 will be utilized for adverse event reporting. (<http://ctep.cancer.gov/reporting/ctc.html>)

Lee 2014 CRS grading criteria: (<https://www.ncbi.nlm.nih.gov/pubmed/24876563>)

Grade	Toxicity
Grade 1	Symptoms are not life threatening and require symptomatic treatment only, eg, fever, nausea, fatigue, headache, myalgias, malaise
Grade 2	Symptoms require and respond to moderate intervention Oxygen requirement <40% or Hypotension responsive to fluids or low dose  of one vasopressor or Grade 2 organ toxicity
Grade 3	Symptoms require and respond to aggressive intervention Oxygen requirement ≥40% or Hypotension requiring high dose* or multiple vasopressors or Grade 3 organ toxicity or grade 4 transaminitis
Grade 4	Life-threatening symptoms Requirement for ventilator support or Grade 4 organ toxicity (excluding transaminitis)
Grade 5	Death

## APPENDIX C. CONTRACEPTIVE GUIDANCE AND PREGNANCY TESTING

### Woman of Childbearing Potential (WOCBP)

A woman is considered fertile following menarche and until becoming post-menopausal unless permanently sterile (see below)

Women in the following categories are not considered WOCBP:

- Premenarchal
  - Premenopausal female with 1 of the following:
    - Documented hysterectomy
    - Documented bilateral salpingectomy
    - Documented bilateral oophorectomy
- Note: Documentation can come from the site personnel's review of the participant's medical records, medical examination, or medical history interview.
- Postmenopausal female
    - A postmenopausal state is defined as no menses for 12 months without an alternative medical cause.
      - A high follicle stimulating hormone (FSH) level in the postmenopausal range may be used to confirm a postmenopausal state in women not using hormonal contraception or hormonal replacement therapy (HRT). However, in the absence of 12 months of amenorrhea, confirmation with two FSH measurements in the postmenopausal range is required.
    - Females on HRT and whose menopausal status is in doubt will be required to use one of the non-hormonal highly effective contraception methods if they wish to continue their HRT during the study. Otherwise, they must discontinue HRT to allow confirmation of postmenopausal status before study enrollment.

### Contraception Requirements

#### Male Participants:

Male participants with female partners of childbearing potential are eligible to participate if they agree to one of the following during the protocol defined time frame in section 5.1:

- Be abstinent from penile-vaginal intercourse as their usual and preferred lifestyle (abstinent on a long term and persistent basis) and agree to remain abstinent
- Use a male condom plus partner use of a contraceptive method with a failure rate of <1% per year as described in Table 12 when having penile-vaginal intercourse with a woman of childbearing potential who is not currently pregnant.
  - Note: Men with a pregnant or breastfeeding partner must agree to remain abstinent from penile-vaginal intercourse or use a male condom during each episode of penile penetration.

**Female Participants:**

Female participants of childbearing potential are eligible to participate if they agree to use a highly effective method of contraception consistently and correctly as described in Table 12 during the protocol-defined time frame in Section 5.1.

**Table 12 Highly Effective Contraception Methods**

Highly Effective Contraceptive Methods That Are User Dependent a Failure rate of <1% per year when used consistently and correctly.

 
● Combined (estrogen- and progestogen- containing ) hormonal contraception b, c 
 
○ Oral
 
○ Intravaginal
 
○ Transdermal
 
○ Injectable
 
 
 

 
● Progestogen-only hormonal contraception b, c 
 
○ Oral
 
○ Injectable
 
 
 

Highly Effective Methods That Have Low User Dependency Failure rate of <1% per year when used consistently and correctly.

 
● Progestogen- only contraceptive implant b, c
 
● Intrauterine hormone-releasing system (IUS) b
 
● Intrauterine device (IUD)
 
● Bilateral tubal occlusion
 

 
● Vasectomized partner  A vasectomized partner is a highly effective contraception method provided that the partner is the sole male sexual partner of the WOCBP and the absence of sperm has been confirmed. If not, an additional highly effective method of contraception should be used. 
 

 
● Sexual abstinence  Sexual abstinence is considered a highly effective method only if defined as refraining from heterosexual intercourse during the entire period of risk associated with the study treatment. The reliability of sexual abstinence needs to be evaluated in relation to the duration of the study and the preferred and usual lifestyle of the participant.) 
 

### **Pregnancy Testing**

WOCBP should only be included after a negative highly sensitive urine or serum pregnancy test and in accordance with local requirements. Schedule as per Flow Chart 7.0

## APPENDIX D. DESCRIPTION OF THE CHESON 2007 CRITERIA FOR ASSESSMENT OF DISEASE RESPONSE

Response criteria were adapted from Cheson 2007 and Lugano 2014.

### CHESON 2007

Refer to Cheson 2007 publication for complete guide on the response criteria. (Cheson et al., 2007). Lugano classification may be consulted for any clarification especially for PET based response assessment.

Table 2. Response Definitions for Clinical Trials				
Response	Definition	Nodal Masses	Spleen, Liver	Bone Marrow
CR	Disappearance of all evidence of disease	(a) FDG-avid or PET positive prior to therapy; mass of any size permitted if PET negative (b) Variably FDG-avid or PET negative; regression to normal size on CT	Not palpable, nodules disappeared	Infiltrate cleared on repeat biopsy; if indeterminate by morphology, immunohistochemistry should be negative
PR	Regression of measurable disease and no new sites	$\geq 50\%$ decrease in SPD of up to 6 largest dominant masses; no increase in size of other nodes (a) FDG-avid or PET positive prior to therapy; one or more PET positive at previously involved site (b) Variably FDG-avid or PET negative; regression on CT	$\geq 50\%$ decrease in SPD of nodules (for single nodule in greatest transverse diameter); no increase in size of liver or spleen	Irrelevant if positive prior to therapy; cell type should be specified
SD	Failure to attain CR/PR or PD	(a) FDG-avid or PET positive prior to therapy; PET positive at prior sites of disease and no new sites on CT or PET (b) Variably FDG-avid or PET negative; no change in size of previous lesions on CT		
Relapsed disease or PD	Any new lesion or increase by $\geq 50\%$ of previously involved sites from nadir	Appearance of a new lesion(s) $> 1.5$ cm in any axis, $\geq 50\%$ increase in SPD of more than one node, or $\geq 50\%$ increase in longest diameter of a previously identified node $> 1$ cm in short axis Lesions PET positive if FDG-avid lymphoma or PET positive prior to therapy	$> 50\%$ increase from nadir in the SPD of any previous lesions	New or recurrent involvement

Abbreviations: CR, complete remission; FDG, [ $^{18}\text{F}$ ]fluorodeoxyglucose; PET, positron emission tomography; CT, computed tomography; PR, partial remission; SPD, sum of the product of the diameters; SD, stable disease; PD, progressive disease.

Table 3. Revised Criteria for Response Assessment		
Response and Site	PET-CT-Based Response	CT-Based Response
Complete	Complete metabolic response	Complete radiologic response (all of the following)
Lymph nodes and extralymphatic sites	Score 1, 2, or 3* with or without a residual mass on 5PS† It is recognized that in Waldeyer's ring or extranodal sites with high physiologic uptake or with activation within spleen or marrow (eg, with chemotherapy or myeloid colony-stimulating factors), uptake may be greater than normal mediastinum and/or liver. In this circumstance, complete metabolic response may be inferred if uptake at sites of initial involvement is no greater than surrounding normal tissue even if the tissue has high physiologic uptake	Target nodes/nodal masses must regress to $\leq 1.5$ cm in LDi No extralymphatic sites of disease
Nonmeasured lesion	Not applicable	Absent
Organ enlargement	Not applicable	Regress to normal
New lesions	None	None
Bone marrow	No evidence of FDG-avid disease in marrow	Normal by morphology; if indeterminate, IHC negative
Partial	Partial metabolic response	Partial remission (all of the following)
Lymph nodes and extralymphatic sites	Score 4 or 5† with reduced uptake compared with baseline and residual mass(es) of any size At interim, these findings suggest responding disease At end of treatment, these findings indicate residual disease	$\geq 50\%$ decrease in SPD of up to 6 target measurable nodes and extranodal sites When a lesion is too small to measure on CT, assign $5 \text{ mm} \times 5 \text{ mm}$ as the default value When no longer visible, $0 \times 0 \text{ mm}$ For a node $> 5 \text{ mm} \times 5 \text{ mm}$ , but smaller than normal, use actual measurement for calculation
Nonmeasured lesions	Not applicable	Absent/normal, regressed, but no increase
Organ enlargement	Not applicable	Spleen must have regressed by $> 50\%$ in length beyond normal
New lesions	None	None
Bone marrow	Residual uptake higher than uptake in normal marrow but reduced compared with baseline (diffuse uptake compatible with reactive changes from chemotherapy allowed). If there are persistent focal changes in the marrow in the context of a nodal response, consideration should be given to further evaluation with MRI or biopsy or an interval scan	Not applicable
No response or stable disease	No metabolic response	Stable disease
Target nodes/nodal masses, extranodal lesions	Score 4 or 5 with no significant change in FDG uptake from baseline at interim or end of treatment	$< 50\%$ decrease from baseline in SPD of up to 6 dominant, measurable nodes and extranodal sites; no criteria for progressive disease are met
Nonmeasured lesions	Not applicable	No increase consistent with progression
Organ enlargement	Not applicable	No increase consistent with progression
New lesions	None	None
Bone marrow	No change from baseline	Not applicable
Progressive disease	Progressive metabolic disease	Progressive disease requires at least 1 of the following PPD progression:
Individual target nodes/nodal masses	Score 4 or 5 with an increase in intensity of uptake from baseline and/or	An individual node/lesion must be abnormal with: LDi $> 1.5$ cm and Increase by $\geq 50\%$ from PPD nadir and An increase in LDi or SDi from nadir 0.5 cm for lesions $\leq 2$ cm 1.0 cm for lesions $> 2$ cm In the setting of splenomegaly, the splenic length must increase by $> 50\%$ of the extent of its prior increase beyond baseline (eg, a 15-cm spleen must increase to $> 16$ cm). If no prior splenomegaly, must increase by at least 2 cm from baseline
Extranodal lesions	New FDG-avid foci consistent with lymphoma at interim or end-of-treatment assessment	New or recurrent splenomegaly New or clear progression of preexisting nonmeasured lesions
Nonmeasured lesions	None	

Table 3. Revised Criteria for Response Assessment (continued)		
Response and Site	PET-CT-Based Response	CT-Based Response
New lesions	New FDG-avid foci consistent with lymphoma rather than another etiology (eg, infection, inflammation). If uncertain regarding etiology of new lesions, biopsy or interval scan may be considered	Regrowth of previously resolved lesions A new node $> 1.5$ cm in any axis A new extranodal site $> 1.0$ cm in any axis; if $< 1.0$ cm in any axis, its presence must be unequivocal and must be attributable to lymphoma Assessable disease of any size unequivocally attributable to lymphoma
Bone marrow	New or recurrent FDG-avid foci	New or recurrent involvement

Abbreviations: 5PS, 5-point scale; CT, computed tomography; FDG, fluorodeoxyglucose; IHC, immunohistochemistry; LDi, longest transverse diameter of a lesion; MRI, magnetic resonance imaging; PET, positron emission tomography; PPD, cross product of the LDi and perpendicular diameter; SDi, shortest axis perpendicular to the LDi; SPD, sum of the product of the perpendicular diameters for multiple lesions.

\*A score of 3 in many patients indicates a good prognosis with standard treatment, especially if at the time of an interim scan. However, in trials involving PET where de-escalation is investigated, it may be preferable to consider a score of 3 as inadequate response (to avoid undertreatment). Measured dominant lesions: Up to six of the largest dominant nodes, nodal masses, and extranodal lesions selected to be clearly measurable in two diameters. Nodes should preferably be from disparate regions of the body and should include, where applicable, mediastinal and retroperitoneal areas. Non-nodal lesions include those in solid organs (eg, liver, spleen, kidneys, lungs). GI involvement, cutaneous lesions, or those noted on palpation. Nonmeasured lesions: Any disease not selected as measured, dominant disease and truly assessable disease should be considered not measured. These sites include any nodes, nodal masses, and extranodal sites not selected as dominant or measurable or that do not meet the requirements for measurability but are still considered abnormal, as well as truly assessable disease, which is any site of suspected disease that would be difficult to follow quantitatively with measurement, including pleural effusions, ascites, bone lesions, leptomeningeal disease, abdominal masses, and other lesions that cannot be confirmed and followed by imaging. In Waldeyer's ring or in extranodal sites (eg, GI tract, liver, bone marrow), FDG uptake may be greater than in the mediastinum with complete metabolic response, but should be no higher than surrounding normal physiologic uptake (eg, with marrow activation as a result of chemotherapy or myeloid growth factors).

†PET 5PS: 1, no uptake above background; 2, uptake  $\leq$  mediastinum; 3, uptake  $>$  mediastinum but  $\leq$  liver; 4, uptake moderately  $>$  liver; 5, uptake markedly higher than liver and/or new lesions; X, new areas of uptake unlikely to be related to lymphoma.

## APPENDIX E. DATA AND SAFETY MONITORING PLAN

### Type of Clinical Trial:

- |  |   |
|--|---|
|  Investigator-initiated (UI/HCCC) |  Investigator-initiated, participating site |
|  Pilot study                                 |  Phase I                                    |
|  Phase I/II                       |  Phase II                                   |
|  Phase III                                   |  Compassionate-use/Expanded Access          |
|  Interventional Treatment         |  Interventional Non-Treatment               |
|  Non-Interventional                          |   |

### Study risk-level:

- ☐ Level 1—low risk of morbidity or death, \* <1% of death or any adverse event
- ☐ Level 2—risk of death\* <1% or any adverse event 1% – 5%
- ☐ Level 3—risk of death\* 1% – 5% or grade 4 – 5 SAE 1% – 5%
- ☒ Level 4—risk of death\* >5% or grade 4 – 5 SAE >5%
- ☐ Drugs being used on a “compassionate” basis

*\* Risk of death” refers specifically to 100-day treatment-related mortality*

---

### Reporting and Monitoring Requirements:

All institutional investigator initiated trials (IITs), regardless of assigned risk level are subject to routine DSMC monitoring activities which may include but are not limited to review of signed consent documents, eligibility and adverse event reporting.

All institutional IITs have the following **reporting requirements** as part of their DSMP:

- Register all subjects in HCCC’s Clinical Trial Management System, OnCore
- Document Adverse Events
- Document protocol deviations
- Provide an annual progress report to the DSMC via OnCore data export

### Selected monitoring strategy based on risk-level:

**Risk Level 4**

Interventional treatment trials involving investigational agents or devices with a risk of death\* (>5% or grade 4 – 5 SAE >5%), e.g. all investigator initiated INDs, most Phase I/II trials, gene therapy, gene manipulation or viral vector systems high-risk clinical procedures if performed solely for research purposes. The use of a new chemical or drug for which there is limited or no available safety data in humans.

**Study Safety Review**

An independent study monitor and/or the DSMC Chair (or designee), will review study data (provided by the PI/available in OnCore) and communicate with the PI at least biannually. A copy of this communication will be forwarded to the DSMC and PRMC Chairs.

**Additional Reporting Requirements:**

- A scanned copy of the completed eligibility checklist, with screening information and PI signature, will be attached in OnCore for ongoing review by DSMC staff.
- Serious adverse events will be entered directly into an OnCore SAE report by the research team. OnCore will send an automatic notification to the DSMC Chair/acting Chair and staff for review.
- The DSMC utilizes a risk-based monitoring approach. The trial's research records will be monitored at minimum twice per year. Monitoring may be done more frequently depending on the protocol, risks to subjects, reported serious/adverse events, patient population and accrual rate. Records for a minimum of 25% of subjects will be monitored for the entire study.

Monitoring will involve the following:

- review eligibility of patients accrued to the study,
- check for the presence of a signed informed consent,
- determine compliance with protocol's study plan,
- determine whether SAEs are being appropriately reported to internal and external regulatory agencies,
- compare accuracy of data in the research record with the primary source documents,
- review investigational drug processing and documentation,
- assess cumulative AE/SAE reports for trends and compare to study stopping rules.

**Routine Adverse Event Reporting**

For non-serious Adverse Events, documentation must begin after the subject signs the Informed Consent Document until 30 days after the last dose of CMP-001. Collected information should be recorded in the electronic/Case Report Forms (eCRF/CRF) for that subject. A description of the event, its severity or toxicity grade (according to [NCI's Common Toxicity Criteria \(CTCAE\)](#)),

onset and resolved dates (if applicable), and the relationship to the study drug should be included. Documentation should occur in real time. The principal investigator has final responsibility for determining the attribution of the event as it is related to the study drug.

### Serious Adverse Event Reporting

For any experience or condition that meets the definition of a serious adverse event (SAE), recording of the event must begin after signing of the informed consent and continue through the 30 days after the last dose of CMP-001.

Investigators must report to the DSMC any serious adverse events (SAE), whether or not they are considered related to the investigational agent(s)/intervention (21 CFR 312.64). SAEs must be reported via an OnCore SAE Report within 24 hours of learning of the event.

An adverse event is considered **serious** if it results in ANY of the following outcomes:

1. Death
2. A life-threatening adverse event
3. An adverse event that results in inpatient hospitalization OR prolongation of existing hospitalization for  $\geq 24$  hours
4. A persistent or significant incapacity or substantial disruption of the ability to conduct normal life functions
5. A congenital anomaly/birth defect.
6. Important Medical Events (IME) that may not result in death, be life threatening, or require hospitalization may be considered serious when, based upon medical judgment, they may jeopardize the patient or subject and may require medical or surgical intervention to prevent one of the outcomes listed in this definition. (FDA, [21 CFR 312.32](#); [ICH E2A](#) and [ICH E6](#)).

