## 7.0 TRIAL FLOW CHART

Procedure or Assessment	Screening (Day -21 to -1) a	W1 D1	W2 D1	W3 D1	W4 D1	W5 D1	W6 D1	W7 D1	W10 D1	Every 3 Weeks Post W10 (W13, W16 etc.)	End of Treatment b	30 Day Follow up visit n	Long Term Survival Follow-up o
CMP-001 Dose Number	n/a	1	2	3	4	5	6	7	8	9+	n/a	n/a	n/a
Visit Windows	n/a	n/a	±2 days	±2 days	±2 days	±2 days	±2 days	±2 days	±7 days	±7 days	±7 days	±7 days	± 1 month
Informed Consent	X												
Eligibility Criteria Assessment	X												
Medical History, Demographics, Cancer History including Prior Cancer Medications	X												
Physical Exam c	X	X		X	X			X	X	X	X		
Vital Signs d	X	X	X	X	X	X	X	X	X	X	X		
ECOG Performance Status	X	X		X	X			X	X	X	X		
Body Weight	X	X			X			X	X	X	X		
Height	X												
Electrocardiogram (ECG) e	X	X		X				X			X		
Autoimmune lab panel f	X										X		
Clinical Laboratory Tests (hematology, serum chemistry, urinalysis) g	X	X	X	X	X	X	X	X	X	X	X		
Coagulation Tests (PTT & INR) h		X						X	X	X			
Thyroid Function Tests	X			X				X			X		
Research blood Samples i	X	X		X			X		X	-			
Tumor Biopsy j	X			X			X		X	-			
Urine Pregnancy Test k	X	X			X			X	X	X	X		
Disease Assessment (PET-CT/CT) a, l	X	At W7D1 (or two cycles) and then as clinically indicated											
Adverse Event Monitoring n		Assessed continually from W1D1 through EOT +30 days											
Concomitant Medications		Assessed continually from 28 days prior to first CMP-001 dose through EOT +30 days											
CMP-001 dosing m		X	X	X	X	X	X	X	X	X			
Pembrolizumab Dosing		Pembrolizumab will be given according to pembrolizumab label (every 3 week)											

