**Footnotes for Trial Flow Sheet:**

- a. Computed tomography (CT neck/chest/abdomen/pelvis with contrast) or PET-CT scans may be performed  $\leq 3$  weeks prior to first CMP-001 dose but up to 4 weeks will be acceptable. MRI will only be considered in specific situation if needed.
- b. End-of-treatment (EOT) assessments to be performed within 7 days following removal of subject from CMP-001 treatment. Removal of a subject from CMP-001 treatment is defined as the time in which the Investigator decides to discontinue CMP-001 treatment for a subject.
- c. A full physical exam will be conducted at Screening and EOT. The Screening physical exam may be performed up to 72 hours prior to the Week 1 Day 1 (W1D1) visit. If the full physical exam is performed  $>72$  hours prior to the W1D1 visit, then a brief (symptom directed) physical exam must be performed within 72 hours prior to initiation of CMP-001.
- d. For the first five CMP-001 dosing visits, vital signs are to be collected prior to CMP-001 dosing, and at 30 ( $\pm 15$ ) minute intervals for 4 hours post end of CMP-001 dosing. Based upon the discretion of the Investigator, observation periods can be reduced to 1 hour for individual subjects who demonstrate mild to no adverse events. Reduced observation periods can be implemented only after the 6th dose of CMP-001. Vital signs should be performed prior to collection of clinical laboratory tests when they are performed at the same visit. On days that CMP-001 and Pembrolizumab are both given, vital signs should be collected following the administration of CMP-001. When CMP-001 intratumoral injection and pembrolizumab dosing fall on the same day, it is recommended that CMP-001 intratumoral injection precede pembrolizumab dosing.
- e. Electrocardiograms (ECGs) should be obtained at Screening and prior to CMP-001 intratumoral injection at the 1st, 3rd, and 7th CMP-001 injection (on W1D1, W3D1, W7D1), and EOT visit.
- f. Autoimmune lab panel to be collected at Screening and EOT. Table 9
- g. Clinical laboratory tests may be performed up to 72 hours prior to administration of CMP-001.
- h. Partial thromboplastin time (PTT) and international normalized ratio (INR) tests should be obtained, and results reviewed as per schedule above. These may be obtained up to 72 hours prior to administration of CMP-001.

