- n. The 30-Day Follow-up (+7 Days) or before new treatment is started is a safety follow up visit that may be conducted in the study clinic OR via phone. The subject should be questioned for any new AEs or ConMeds, no other safety assessments are required unless the Investigator identifies a new safety concern that requires further follow-up. This visit should occur 30 days (+7) after the EOT visit. SAEs that occur within 90 days of the end of treatment or before initiation of a new anti-cancer treatment, whichever comes first should also be followed and recorded.
- o. All subjects will be followed for survival for 2 years ( $3 \pm 1$  month). Survival follow up may be accomplished by visit or phone contact for two years or until subject death, subject consent is withdrawn, subject is lost to follow up or the study is completed.

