## 8.2 Assessing and Recording Adverse Events

An adverse event is defined as any untoward medical occurrence in a patient or clinical investigation participant administered a pharmaceutical product and which does not necessarily have to have a causal relationship with this treatment. An adverse event can therefore be any unfavorable and unintended sign (including an abnormal laboratory finding, for example), symptom, or disease temporally associated with the use of a medicinal product or protocol-specified procedure, whether or not considered related to the medicinal product or protocol-specified procedure. Any worsening (i.e., any clinically significant adverse change in frequency and/or intensity) of a preexisting condition that is temporally associated with the use of the Merck's product, is also an adverse event.

Changes resulting from normal growth and development that do not vary significantly in frequency or severity from expected levels are not to be considered adverse events. Examples of this may include, but are not limited to, teething, typical crying in infants and children and onset of menses or menopause occurring at a physiologically appropriate time.

Merck product includes any pharmaceutical product, biological product, device, diagnostic agent or protocol-specified procedure, whether investigational (including placebo or active comparator medication) or marketed, manufactured by, licensed by, provided by or distributed by Merck for human use.

Adverse events may occur during the course of the use of Merck product in clinical trials, or as prescribed in clinical practice, from overdose (whether accidental or intentional), from abuse and from withdrawal.

- All AEs from Week 1 Day 1 (treatment initiation) through 30 days following cessation of study treatment must be reported by the investigator.
- All AEs meeting serious criteria, from the time of treatment allocation/randomization through 90 days following cessation of study treatment, or 30 days following cessation of study treatment if the participant initiates new anticancer therapy, whichever is earlier must be reported by the investigator.
- All pregnancies and exposure during breastfeeding, from the time of treatment allocation/randomization through 120 days following cessation of study treatment, or 30 days following cessation of study treatment if the participant initiates new anticancer therapy must be reported by the investigator.

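### Appendix E and flow-chart footnote b time safety collection from CMP-001 alone, while Sections 5.5, 8.1.7.4 and 8.2 use all study treatment; the SAE end dates differ by at least 60 days when no new therapy starts

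*Combined protocol and SAP*

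**What the plan says.** The document holds two sets of rules.

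**Timed from CMP-001.**
- Appendix E, Serious Adverse Event Reporting: "recording of the event must begin after signing of the informed consent and continue through the 30 days after the last dose of CMP-001".
- Appendix E, Routine Adverse Event Reporting: "documentation must begin after the subject signs the Informed Consent Document until 30 days after the last dose of CMP-001".
- Section 7.0, footnote b, places the EOT assessments within 7 days of removal from CMP-001, and adds: "Removal of a subject from CMP-001 treatment is defined as the time in which the Investigator decides to discontinue CMP-001 treatment for a subject".
- The flow chart's adverse event row depends on that EOT: "Assessed continually from W1D1 through EOT +30 days".

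**Timed from study treatment.**
- Section 8.2, all AEs: "through 30 days following cessation of study treatment must be reported by the investigator".
- Section 8.2, SAEs: "through 90 days following cessation of study treatment, or 30 days following cessation of study treatment if the participant initiates new anticancer therapy", taking the earlier of the two.
- Section 8.1.7.4 sets the safety visit about 30 days after the last study treatment dose and also gives 90 days for SAEs.
- Section 5.5 asks for EOT assessments once study treatment has stopped. It lists reaching 35 pembrolizumab treatments as a reason to stop, so study treatment includes pembrolizumab.

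Footnote n has the longer SAE period, "SAEs that occur within 90 days of the end of treatment or before initiation of a new anti-cancer treatment, whichever comes first", but sits in the flow chart whose EOT is defined by CMP-001.

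Section 6.1.2 lets pembrolizumab continue with or without injection when no site can be injected after the Week 7 scan. Section 6.2 allows one drug to be modified alone when a toxicity is more clearly related to it. No text says which set of rules takes precedence.

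**The concern.** These are rules that contradict each other, not missing detail. They differ in two ways:

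- **Length.** Appendix E stops SAE recording at 30 days, against 90 in the body. This needs no unusual treatment path. It applies to a patient who stops both drugs on the same day and starts no other therapy.
- **Starting point.** If CMP-001 ends and pembrolizumab continues, Appendix E applied as written closes documentation while an active study drug is still being given. Footnote b triggers EOT in the same situation.

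Describing the safety of the combination is a secondary objective (Section 3.2), and Section 6.2.2 notes that immune-related events can appear months after the last pembrolizumab dose. Appendix E rates the study at risk level 4 and has monitors check that SAEs are properly reported and compare cumulative events with the stopping rules. It also states: "Investigators must report to the DSMC any serious adverse events (SAE), whether or not they are considered related to the investigational agent(s)/intervention". A monitor with two end dates cannot apply that check consistently. An unrelated SAE on days 31 to 90 after both drugs stop, in a patient on no new therapy, is required by Section 8.2 but lies outside Appendix E's recording period.

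**Working it through.** The plan has no figure of its own to reproduce. The check is date arithmetic.

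**Inputs.** Appendix E: last CMP-001 dose + 30 days, for AEs and SAEs. Section 8.2: cessation of study treatment + 30 days for AEs; + 90 days for SAEs, or + 30 if new anticancer therapy starts. Pembrolizumab is given every 3 weeks, to a maximum of 35 doses (Section 5.5). Average treatment is 6 months (Section 1.0), taken as 182 days.

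**Assumptions.** Cessation is the date of the last dose of either drug. Pembrolizumab starts at W1D1, so dose k falls on day 1 + 21(k − 1). Nine doses then fall by day 182, the ninth on day 169; dose 35 is on day 715. W7D1 is day 43, W10D1 day 64 and W13D1 day 85.

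**Formulas.** Let C be the day of the last CMP-001 dose, and L the lag from C to the last dose of either drug (0 if CMP-001 is last).
- SAE gap, no new therapy: (C + L + 90) − (C + 30) = 60 + L.
- SAE gap, new therapy: (C + L + 30) − (C + 30) = L.
- Non-serious AE gap: (C + L + 30) − (C + 30) = L.

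| Last CMP-001 | Last pembrolizumab | L | Appendix E closes | 8.2 AE end | 8.2 SAE end | AE gap | SAE gap, no new therapy | Pembrolizumab doses after Appendix E closes |
|---|---|---|---|---|---|---|---|---|
| day 64 | day 64 | 0 | 94 | 94 | 154 | 0 | 60 | 0 of 4 |
| day 43 | day 64 | 21 | 73 | 94 | 154 | 21 | 81 | 0 of 4 |
| day 43 | day 85 | 42 | 73 | 115 | 175 | 42 | 102 | 1 of 5 |
| day 64 | day 169 | 105 | 94 | 199 | 259 | 105 | 165 | 4 of 9 |
| day 43 | day 169 | 126 | 73 | 199 | 259 | 126 | 186 | 5 of 9 |
| day 43 | day 715 | 672 | 73 | 745 | 805 | 672 | 732 | 31 of 35 |

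Starting pembrolizumab at W2D1 (day 8) leaves the 5 of 9 and 4 of 9 counts unchanged.

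**Flow chart.** A decision at W7D1 to stop CMP-001, with EOT the same day, ends AE monitoring on day 43 + 30 = 73. A decision at W10D1 with EOT 7 days later ends it on day 64 + 7 + 30 = 101. These are examples, not limits, because the date depends on when the decision is made.

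**Effect of partial repairs.** Changing only Appendix E's starting point leaves an SAE gap of 90 − 30 = 60 days. Changing only its length leaves L. Changing both leaves 0.

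**The case against.** The best reply is that the duties add up rather than compete. Section 8.2 serves reporting to the sponsor and the manufacturer; Appendix E is the institution's monitoring plan. Appendix E requires recording through day 30 and does not forbid it later. Section 8.2, footnote n and Section 8.1.7.4 all require the longer SAE period, and drug-related SAEs are reportable at any time. Staff who follow the widest window satisfy everything. The sentence on DSMC reporting, and the one on entering SAEs in OnCore, carry no end date, so a late unrelated SAE arguably falls under them.

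Most of this stands, and it rules out several stronger readings that a reader might infer:

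- *That SAEs on days 31 to 90 go uncollected.* The protocol body requires them.
- *That Appendix E's SAE window is 60 days shorter overall.* The 60 days concerns the end date. Appendix E opens at consent and Section 8.2 at allocation. If consent comes 21 days earlier (assumed from the Day −21 screening start), total lengths differ by 60 − 21 = 39 days when both drugs stop together.
- *That the gap is always 60 days, or always 0 after new therapy.* Both hold only when L is 0.
- *That having no injectable lesion triggers EOT.* Section 6.1.2 allows injection of the tumor bed to continue, and footnote b needs a decision to stop CMP-001.

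The objection does not supply a rule of precedence. Using the widest window is sensible, but no text instructs it. Nor does it reconcile footnote b with Section 5.5, which place the same EOT assessments at different times for a patient continuing pembrolizumab.

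**Conclusion.** The conflict is real and should be corrected. Without new anticancer therapy, Appendix E's SAE end date precedes Section 8.2's by 60 days plus the lag, so by at least 60. With new therapy the gap equals the lag, as does the non-serious AE gap in every case. The scenario figures rest on the assumed dosing dates. The documents do not say how many patients will continue pembrolizumab alone, and none is estimated here; the 60-day minimum does not depend on that number.

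The consequence is limited to uncertainty over which end date governs the AE record, the OnCore and DSMC record of SAEs, and EOT. A reader might infer that the dose-finding result is compromised. The documents do not support this: the 15-day DLT period and the Week 7 response scan both finish before any of these windows closes in the scenarios above.

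The body also disagrees with itself on new therapy. Footnote n and Section 8.1.7.4 stop SAE collection when the new treatment starts, whereas Section 8.2 stops it 30 days after study treatment ends.

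**What to change.** 1. In both Appendix E paragraphs, count from the last dose of CMP-001 or pembrolizumab, whichever is later.
2. In the Appendix E SAE paragraph, replace 30 days with Section 8.2's period: 90 days, or 30 days if new anticancer therapy starts, whichever is earlier. Put the same new-therapy rule in footnote n and Section 8.1.7.4.
3. In footnote b, define EOT as discontinuation of both drugs. Keep pembrolizumab-only patients on AE monitoring and on the flow chart's every-3-week column, without the injection.

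Edits 1 and 2 are both needed to close the SAE gap. They cost wording changes and OnCore entry of SAEs that Section 8.2 already requires.

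Edit 3 costs more than wording. Patients on pembrolizumab alone would have the column's assessments at their pembrolizumab visits: examination, vital signs, performance status, weight, laboratory tests, PTT/INR and, where applicable, pregnancy testing. Their EOT ECG, autoimmune panel and thyroid tests would come later, up to about two years for a patient completing 35 doses. The flow chart schedules none of those three between Week 7 and EOT, so the sponsor should accept that delay knowingly.

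These edits leave the different opening dates as they are. Non-serious events more than 30 days after the last dose of either drug stay outside both windows.
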